1.1.2 Hormone-sensitive breast cancer

More than two thirds of all advanced breast cancers are dependent on estrogen. Estrogen withdrawal by physical removal of the ovaries or inhibition of their function has been one of the earliest successful interventions against breast cancer; however this intervention was limited to premenopausal women. The introduction of the SERMS (selective estrogen receptor modulators) has dramatically improved the survival of women with breast cancer, both pre and postmenopausal. The most prominent SERM is tamoxifen, which until recently has been the gold standard for first-line therapy in women with advanced hormone-sensitive breast cancer. The production of estrogen in postmenopausal women requires an enzyme called aromatase, which can be successfully blocked chemically. The introduction of several aromatase inhibitors (AIs) has added greatly to the arsenal against breast cancer and they have replaced tamoxifen as first-line therapy in the postmenopausal setting. The most commonly used aromatase inhibitors include letrozole, anastrozole and exemestane.

However, the AIs are reserved for women who have naturally entered menopause or have their ovarian function suppressed. For premenopausal women or women who are unable to tolerate AIs, tamoxifen remains the gold standard.

The response rate to first line hormonal therapy, determined from four pivotal randomized Phase III trials, ranges from 20-33%^{10,11,12,13}. The response rate to second line hormonal therapy is considerably less (10-20%)¹⁰, suggesting a clear need for more effective therapy.^{14,15,16}

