In a Phase II clinical trial, we evaluated the role of vorinostat (VOR) in reversing hormone therapy resistance in advanced breast cancer². In a single arm study, 43 patients (median age 56 years (31–71)) were treated. A total of 25 patients (58%) received prior adjuvant tamoxifen (TAM), 29 (67%) progressed on at least one prior chemotherapy regimen, 42 (98%) progressed after one, and 23 (54%) after two aromatase inhibitors. The objective response rate by RECIST criteria was 19% and the clinical benefit rate (response or stable disease \geq 24 weeks) was 40%. The median response duration was 10.3 months (confidence interval: 8.1–12.4). Histone hyperacetylation and higher baseline HDAC2 levels correlated with response and responses were mainly seen in the 56% of patients who had a meaningful change in acetylation with vorinostat. Preclinical studies have further suggested that hormonal therapy must be continued even in the presence of an HDAC inhibitor.

1.3.1.2 Prior studies with other HDAC inhibitors in breast cancer:

[figure not shown]
A second phase II (ENCORE 301) trial evaluated entinostat and exemestane, and treated patients with advanced estrogen receptor (ER)-positive breast cancer⁶⁶. This study recently received Breakthrough Therapy designation from the FDA for its potential to reverse resistance to hormonal therapies. The median PFS was 4.3 months versus 2.3 months, for entinostat and placebo, respectively (HR = 0.73; P = 0.06). The median overall survival in the combination arm was 28.1 m compared to 19.8 m in the exemestane arm (HR = 0.59; P = 0.036). The objective response rate to the combination was 6.3%, while to exemestane alone was 4.6% (P = 0.58). While these two studies cannot be compared directly, the preclinical studies and the clinical studies, as well as the current landscape of standard of care, will make the combination with tamoxifen more likely effective. The combination with tamoxifen will also allow enrollment of premenopausal women.

Hence the combination of HDAC inhibitors and PD-1 inhibitors may further result in an enhancement of anti-tumor efficacy of PD-1 inhibitors^{6,67}. Based on the established role of HDAC inhibitors in reversing hormone therapy resistance to antiestrogens and aromatase

inhibitors and the provocative role of HDAC inhibitors in modulating tumor immunity, we propose to test the role of epigenetic immune priming (EIP) in acquired hormone therapy resistance.

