3.3.1 Inclusion Criteria

1. Pre and postmenopausal women or men with stage IV ER+ breast cancer histological or cytological confirmation

ER-positive tumors

- a. Progressed after at least one line of hormonal therapy

- b. Any number of prior chemotherapy in the metastatic setting
- c. Any number of prior hormonal therapies.
- d. HER2 positive or negative

ER-negative tumors

- e. PD-L1 low, high or unknown
 - f. Progression after prior PD-1 or PD-L1 inhibitors allowed
 - g. HER2 positive or negative
2. 18 years or older.
 3. Eastern Cooperative Oncology Group (ECOG) Performance Status of ≤ 2 .
 4. Understand and voluntarily sign an informed consent prior to any study-related assessments or procedures are conducted and are able adhere to the study visit schedule and other protocol requirements.
 5. Consent to paired tumor biopsy, for accessible tumors
 6. Measureable tumor by RECIST criteria v.1.1
 7. Per Good Clinical Practice, any toxicity related to prior therapies that, in the opinion of the investigator, would potentially be worsened with anti-PD1 therapy should be resolved to less than Grade 1
 8. Adequate organ function within 14 days of study start:
 - o Absolute neutrophil count (ANC) $\geq 1.5 \times 10^9/L$
 - o Hemoglobin (Hgb) $\geq 9g/dL$ (may transfuse if clinically indicated)
 - o Platelets (plt) $\geq 100 \times 10^9/L$
 - o Potassium within normal range, or correctable with supplements;
 - o AST and ALT $\leq 2.5 \times$ Upper Limit Normal (ULN) or $\leq 5.0 \times$ ULN if liver tumor is present;
 - o Serum total bilirubin $\leq 1.5 \times$ ULN
 - o Serum creatinine $\leq 1.5 \times$ ULN, or 24-hr clearance $\geq 60ml/min$; and
 9. Females of child-bearing potential (defined as a sexually mature women who):
 - o Has not undergone a hysterectomy (the surgical removal of the uterus) or bilateral oophorectomy (the surgical removal of both ovaries) or,
 - o Has not been naturally postmenopausal for at least 24 consecutive months (i.e., has had menses at any time during the preceding 24 consecutive months).

Must have negative serum pregnancy test within 7 days before starting study treatment in females of childbearing potential (FCBP) and willingness to adhere to acceptable forms or birth control (a physician- approved contraceptive method (oral, injectable, or implantable hormonal contraceptive; tubal ligation; intra-uterine device; barrier contraceptive with spermicide; or vasectomized partner).

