- Management of Infusion Reactions: Acute infusion reactions (which can include cytokine release syndrome, angioedema, or anaphylaxis) are different from allergic/hypersensitive reactions, although some of the manifestations are common to both AEs. Signs and symptoms usually develop during or shortly after drug infusion and generally resolve completely within 24 hours of completion of infusion. Signs/symptoms may include: Allergic reaction/hypersensitivity (including drug fever); Arthralgia (joint pain); Bronchospasm; Cough; Dizziness; Dyspnea (shortness of breath); Fatigue (asthenia, lethargy, malaise); Headache; Hypertension; Hypotension; Myalgia (muscle pain); Nausea; Pruritis/itching; Rash/desquamation; Rigors/chills; Sweating (diaphoresis); Tachycardia; Tumor pain (onset or exacerbation of tumor pain due to treatment); Urticaria (hives, welts, wheals); Vomiting.

Contraception

Pembrolizumab, tamoxifen and vorinostat may have adverse effects on a fetus in utero. Furthermore, it is not known if pembrolizumab has transient adverse effects on the composition of sperm. Non-pregnant, non-breast-feeding women may be enrolled if they are willing to use 2 methods of birth control or are considered highly unlikely to conceive. Highly unlikely to conceive is defined as 1) surgically sterilized, or 2) postmenopausal (a woman who is ≥ 45 years of age and has not had menses for greater than 1 year will be considered postmenopausal), or 3) not heterosexually active for the duration of the study. The two birth control methods can be either two barrier methods or a barrier method plus a hormonal method to prevent pregnancy. Subjects should start using birth control from study Visit 1 throughout the study period up to 120 days after the last dose of study therapy.

The following are considered adequate barrier methods of contraception: diaphragm, condom (by the partner), intrauterine device, sponge, or spermicide. Appropriate hormonal contraceptives will include any registered and marketed contraceptive agent that contains an estrogen and/or a progestational agent (including oral, subcutaneous, intrauterine, or intramuscular agents).

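### Section 6.3.4 accepts any estrogen-containing contraceptive, with no exception for premenopausal ER+ patients taking daily tamoxifen in Arms A and B

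*Combined protocol and SAP*

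**What the plan says.** Section 6.3.4 (Contraception) asks women who could conceive to use two methods: two barrier methods, or one barrier and one hormonal method. It then defines the acceptable hormonal products as "any registered and marketed contraceptive agent that contains an estrogen and/or a progestational agent", by several routes. The definition does not vary by arm, ER status or tamoxifen use.

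Inclusion criterion 9 (section 3.3.1) asks for a physician-approved method. Its list opens with "oral, injectable, or implantable hormonal contraceptive" and ends with "barrier contraceptive with spermicide; or vasectomized partner". It too draws no line by ER status.

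The population is set by inclusion criterion 1, "Pre and postmenopausal women or men with stage IV ER+ breast cancer", with ER+ patients having progressed after at least one line of hormonal therapy. Section 1.3 gives access for younger women as a benefit of the regimen: "The combination with tamoxifen will also allow enrollment of premenopausal women". Table 5.1 and Table 6 give tamoxifen 20 mg daily without interruption in Arms A and B, and none in Arm C.

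**The concern.** A premenopausal woman with ER+ disease can meet every written rule while taking estrogen together with the antiestrogen that is part of her trial treatment. The protocol's background points the other way. Section 1.1.2 puts the share of advanced breast cancers that depend on estrogen above two thirds and says that "Estrogen withdrawal by physical removal of the ovaries or inhibition of their function has been one of the earliest successful interventions against breast cancer". Section 1.2.1 names thromboembolism as tamoxifen's most serious side effect. Section 6.3.4 itself gives tamoxifen as one reason why contraception is needed, and then accepts estrogen as a way to provide it.

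What is at stake is the safety of individual patients. A rule that calls these products appropriate tells site staff and outside prescribers that they are acceptable, and the protocol provides for participating sites beyond the coordinating center (section 9.4, Appendix 4).

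**Working it through.** The plan states no figure on this point, so the check is a reading of the rules, followed by a note on numbers.

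1. **Does the permission reach patients on tamoxifen?** Inclusion 1 admits premenopausal ER+ women. Tables 5.1 and 6 give them daily tamoxifen. Section 6.3.4 and inclusion 9 apply to all arms. Yes.

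2. **Does any other rule remove it?** Section 3.3.2 has 18 exclusion criteria and section 6.3.3 lists 7 prohibited therapies: 18 + 7 = 25 entries, of which 0 name estrogens. The tamoxifen section (4.1.1) gives no such restriction either.

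3. **What discretion remains?**
   - Inclusion 9: the method must be physician-approved.
   - Exclusion 1: conditions that put the subject at unacceptable risk.
   - Exclusion 4: conditions that confound interpretation of the data.
   - Exclusion 12: conditions or therapies that might confound results, or participation not in the subject's best interest, in the investigator's opinion.
   - Section 6.2.3: the investigator withdraws a patient whose continued participation no longer serves her.

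   Each depends on one clinician's judgment. None mentions estrogen or contraception in ER+ disease.

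4. **A worked case.** A premenopausal ER+ woman uses a condom and a combined pill approved by her physician. Section 6.3.4 is met (one barrier, one hormonal). Inclusion 9 is met. None of the 25 entries names her pill.

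5. **Is estrogen needed for compliance?** No. Two barrier methods satisfy 6.3.4, so an exclusion removes nothing that the trial requires.

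6. **How many women?** The documents give no share of premenopausal women. Section 3.1 gives the size of the tamoxifen arms: 10 + 10 = 20 in Stage 1 and 29 + 29 = 58 at full size. These are ceilings that include men and postmenopausal women. As a pure assumption, if 5% to 30% were premenopausal women needing contraception, the permission would cover 0.05 × 20 = 1 to 0.30 × 20 = 6 in Stage 1, and 0.05 × 58 = 2.9 to 0.30 × 58 = 17.4 at full size. Nothing in the documents anchors that range, and it counts women covered, not users of estrogen. Indirect evidence suggests that the upper end is too high. In the earlier vorinostat–tamoxifen trial (section 1.3.1.1) the median age was 56, and 42 of 43 patients had progressed after an aromatase inhibitor, a class that section 1.1.2 reserves for women in natural menopause or with suppressed ovaries.

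**The case against.** The strongest reply is that this will hardly ever happen. Every ER+ patient has metastatic disease that progressed on hormonal therapy, her method needs a physician's approval, and several clauses let the investigator refuse or withdraw her. Section 6.3.4 says which methods count; it directs nobody to take estrogen. All of that stands, and it makes actual use unlikely. It does not remove the permission: the discretionary clauses work only if the clinician overrides a text that calls the product appropriate.

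A second reply is that the rationale is less one-sided than it looks. Section 1.1.1 lists estrogen administration among historical endocrine treatments. Ovarian suppression is allowed but not required (exclusion 2c), so the design tolerates a patient's own estrogen alongside tamoxifen. The statement that "hormonal therapy must be continued even in the presence of an HDAC inhibitor" concerns endocrine treatment, not contraceptives, and nothing here rests on it. The reply is fair in that no passage says contraceptive estrogen harms a patient on tamoxifen; section 1.2.1 describes tamoxifen's own risk only. But estrogen as a historical antitumor treatment, or as ovarian output, is not a reason to approve added estrogen for contraception in a disease that the protocol calls mostly estrogen-dependent.

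A reader might go further and infer that the permission biases the 24-week response rate or weakens the two-stage design. The documents support neither: they give no count of users and no effect size, and the design's error rates do not depend on this rule. A reader might also take 58 as the number at risk; it is only the combined size of two arms.

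Finally, the contraception texts differ in wording. Inclusion 9 asks for a method and section 6.3.4 for two. Inclusion 9 defines childbearing potential partly by "Has not been naturally postmenopausal for at least 24 consecutive months", while 6.3.4 uses age 45 or over with more than one year without menses. Section 6.3.4 also cites section 7.2.2 for pregnancy reporting, where 7.8.3 is evidently meant. These are editorial matters and not part of this point.

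**Conclusion.** The point holds as a safety defect in a stated rule. Section 6.3.4 and inclusion 9 together accept estrogen-containing contraceptives for premenopausal ER+ women on daily tamoxifen, against the protocol's own account of estrogen dependence and of tamoxifen's thromboembolic risk, and only case-by-case judgment stands in the way. Confidence is high that no exception appears in the supplied text. The clinical consequence is an inference from the protocol's premises, not a documented harm. The number of women affected is unknown and probably small, and actual users could be none.

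**What to change.** Add to inclusion criterion 9 and to the Contraception text in 6.3.4: *Estrogen-containing contraceptives are not acceptable for patients with ER+ disease (Arms A and B); use two non-hormonal methods from the list in 6.3.4, and a patient found using such a product switches method.* The sponsor should state explicitly whether progestin-only products, including hormone-releasing intrauterine ones, may be used in these arms. The present wording can stay for Arm C.

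No entry in 6.3.3 is needed. That section removes subjects who require a listed therapy, and it lapses in post-treatment follow-up, while contraception runs to 120 days after the last dose.

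The cost is amendment wording and a check of the consent form, with no extra patients, visits or procedures. The downside is a narrower choice of contraception for premenopausal ER+ women. One who declines two non-hormonal methods could not take part unless the sponsor accepts a progestin-only product.

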7.1 Evaluation of Efficacy (or Activity)

7.1.1. Antitumor Effect

Response and progression in this study will be evaluated using the new international criteria proposed by the Response Evaluation Criteria in Solid Tumors ([RECIST](#)) Committee [JNCI 92(3):205-216, 2000] as well as Immune Related Response-Criteria (irRC). Changes in only the largest diameter (unidimensional measurement) of the tumor lesions are used in the RECIST v1.1 criteria (or [International Workshop on Chronic Lymphocytic Leukemia \[IWCLL\]](#)).

7.1.2 Definitions

Evaluable for toxicity

All patients will be evaluable for toxicity from the time of their first treatment with the study drug.

Evaluable for objective response

Only those patients who have measurable disease present at baseline, have received at least one cycle of therapy, and have had their disease re-evaluated will be considered evaluable for response. These patients will have their response classified according to the definitions stated below. (Note: Patients who exhibit objective disease progression prior to the end of Cycle 1 will also be considered evaluable.)

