3.6 Randomization Procedures

This is an open-label randomized trial; therefore, the Sponsor, investigator and subject will know the treatment administered. Two arms will be tested, with each independent assessment. Patients will be randomized to either arm using a computerized randomization program by [name]. Patients will be further stratified by prior number of chemo- and hormonal therapies.

No randomization is required for ER-negative patients (patients must have biopsiable disease)

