8.0 Statistical Considerations and Evaluation of Results

This trial will determine whether epigenetic priming may enhance the effects of PD-1 inhibitors in patients with ER+ metastatic breast cancer who have progressed on prior hormone therapy and chemotherapy. The trial will contain three arms. Within each arm we will determine whether epigenetic priming will required prolonged pre-exposure to epigenetic modulators or concomitant administration.

Three arms will be tested, with each independent assessment. Patients will be stratified by prior number of hormonal therapy and chemotherapy, then randomized across arms by [name], UCSF.

8.1 Response rates to chemotherapy in breast cancer are less than 20%. Historical response rates to pembrolizumab and MPDL3280A have been 18% and 19%, respectively, in patients whose tumors are PD-L1 positive. Hence, we expect the response rate for unselected patients and patients with no PD-L1 expression would be 10% or less. In contrast, we anticipate that vorinostat will increase the response rate to 30%**Sample Size and Power Estimate**

Response rates to hormonal therapy and MTOR or HDAC inhibitors have been reported as 5-20% (19% for VOR-Tam, 6% for entinostat-exemestane, 12% for exemestane-everolimus). Given the recent additions to hormonal therapy this trial will treat a patient population that has received more lines of therapy than these trials, however we are interested in an ORR of >30%.

8.2 For each arm: Using an Optimal Simon's two-stage design (Simon, 1989), the null hypothesis (H₀) that the true response rate is 10% will be tested against a one-sided alternative. In the first stage, 10 patients will be accrued and a decision will be made to continue or stop accrual based on the observed objective response rate (ORR). If there are 0 or 1 objective responses at 24 weeks in these 10 patients, accrual to this arm of the study will be stopped. Otherwise, 19 additional patients will be accrued for a total of n=29. We estimate that each regimen under evaluation will achieve ORR ≥ 30%. This study is designed to have an alpha of 0.0471, and a power of 80.5% to test the null hypothesis H₀: ORR = 10% against an alternative hypothesis, H_A: ORR = 30%, where ORR is defined as CR, PR, or SD ≥ 24 weeks where arms are enrolled independently.**Interim Analyses**

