8.3 Analyses Plans

8.3.1 Analysis Populations

We will conduct an intention-to-treat analysis of efficacy. All patients who were randomized will be evaluated.

For evaluation of safety, we will restrict the arm-specific samples to all patients who have received at least one dose of investigational therapy.

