8.3.2 Evaluation of Efficacy

For each arm objective response rate (ORR) will be defined as the proportion of participants randomized to that arm whose status is SD or better (CR, PR) at 24 weeks' follow-up. In addition to calculating the ORR, we will calculate the corresponding Agresti-Coull interval 95% confidence interval (CI) (Ref: *Agresti, Alan; Coull, Brent A. (1998). "Approximate is better than 'exact' for interval estimation of binomial proportions". The American Statistician 52: 119–126. doi:10.2307/2685469*). If the lower bound of the 95% CI exceeds 10%, we will reject the null

hypothesis that the regimen is ineffective and conclude that it is sufficiently effective to warrant further study.

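### The evaluable-for-response rule (Section 7.1.2) and a replacement footnote (Section 5.1.1.1) conflict with the intention-to-treat denominator in Section 8.3, whose wording leaves out non-randomised Arm C

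*Combined protocol and SAP*

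**What the plan says.** - **Section 7.1.2, evaluable for objective response.** Besides measurable disease at baseline, patients must "have received at least one cycle of therapy, and have had their disease re-evaluated will be considered evaluable for response". Only these patients have a response classified. The one exception is objective progression before the end of Cycle 1; death is not mentioned.
- **Section 6.1 and Table 6.** The first scheduled restaging is at week 9.
- **Section 5.1.1.1, footnote to the neutropenia table.** Patients delayed by more than 3 weeks in the first two cycles are to be replaced, for efficacy as well as toxicity.
- **Section 8.3.1.** Efficacy is analysed by intention to treat: "All patients who were randomized will be evaluated".
- **Section 8.3.2.** For each arm the ORR is "the proportion of participants randomized to that arm whose status is SD or better (CR, PR) at 24 weeks' follow-up". The regimen succeeds if the lower Agresti-Coull 95% limit exceeds 10%.
- **Section 3.6.** "No randomization is required for ER-negative patients". The introduction to Section 8.0 nevertheless describes randomisation across three arms.
- **Section 8.0, paragraph numbered 8.2.** The two-stage design applies to each arm and counts patients accrued, 10 and then 29. The stage 1 rule is: "If there are 0 or 1 objective responses at 24 weeks in these 10 patients, accrual to this arm of the study will be stopped".

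**The concern.** The plan contains two descriptions of who counts for response and does not say which prevails. It also has no sentence stating that a patient without a post-baseline assessment is a non-responder. Patients lost before the first rescan cannot be recorded as successes, so leaving them out can only raise the rate of a primary endpoint. The replacement footnote is a second route out of the count, and it too acts on patients with early trouble.

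The gap matters most in Arm C. If Section 3.6 is followed, neither population sentence in Section 8.3 describes any ER-negative patient. An analyst could then apply the 7.1.2 set to Arm C and the intention-to-treat set to Arms A and B. Arm C would be reported on a more favourable denominator. If the choice were made after the data were seen, it would be a post hoc decision on the primary endpoint.

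**Working it through.** **Inputs.** From Section 8.2: null rate 10%, alternative 30%, continue with at least 2 of 10, total 29 per arm. From Section 8.3.2: success if the Agresti-Coull lower 95% limit exceeds 10%. The proportion never rescanned is not in the documents; I assume 5%, 10% and 15%.

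**Step 1: reproduce the plan's figures.** The chance of at least *r* responders in 29 after passing stage 1 is Σ(x = 2 to 10) P(X = x) × P(Y ≥ r − x), with X ~ Bin(10, p) and Y ~ Bin(19, p).

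| Cut-off r | p = 10% | p = 30% |
|---|---|---|
| 5 | 0.1016 | 0.8369 |
| 6 | 0.0471 | 0.8051 |
| 7 | 0.0177 | 0.7389 |

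The plan states: "This study is designed to have an alpha of 0.0471, and a power of 80.5" (per cent). Of these cut-offs only r = 6 reproduces both figures.

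**Step 2: apply the written decision rule.** With z = 1.96, let ñ = n + z² and p̃ = (x + z²/2)/ñ. The lower limit is p̃ − z√(p̃(1 − p̃)/ñ).

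- 6/29: ñ = 32.84, p̃ = 0.2412, lower limit 0.2412 − 1.96 × 0.0747 = **9.49%**, fails.
- 6/28: **9.86%**, fails.
- 6/27: ñ = 30.84, p̃ = 0.2568, lower limit 0.2568 − 1.96 × 0.0787 = **10.26%**, passes.
- 7/29: 11.95%, passes already.
- 5/27: 7.72%, still fails.

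The rule needs 7 responders on a denominator of 29 or 28, and 6 on denominators from 27 down to 22. Two is therefore the smallest number of removed patients that changes the conclusion, and with two removed it changes only at exactly 6 responders. The probability of that outcome, including the stage 1 gate, is 0.0471 − 0.0177 = 0.0294 at a true 10% rate.

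**Step 3: average over the number never rescanned.** Let u be the chance that a patient is never rescanned, all such patients being non-responders. Each non-responder is then dropped with probability u/(1 − p). The stage 1 gate stays on all 10 accrued patients, and the final rule uses 29 minus the number dropped.

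| u | Success at true 10% | Success at true 30% |
|---|---|---|
| 0 (all 29 kept) | 1.8% | 73.9% |
| 5% | 2.9% | 77.2% |
| 10% | 4.0% | 79.6% |
| 15% | 4.7% (0.0465) | 80.7% |

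Over this range the false-positive chance stays below 0.0471. It would not do so at any rate: at 20% the same calculation gives 5.4%, because a denominator of 21 or fewer lets 5 responders pass (5/21: 10.23%).

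**The case against.** **Arms A and B are already settled.** Section 8.3.1 names intention to treat, and Section 8.3.2 gives the denominator in the same paragraph as the decision rule. Section 7.1.2 does not use the word denominator. An unevaluable patient can be read as someone without SD or better at 24 weeks who stays in the randomised count. This stands. What remains for these arms is an unreconciled definition, the replacement footnote, and the missing non-responder rule.

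**Arm C has some wording of its own.** A reader might infer that 7.1.2 is the only population text that fits Arm C. It is not: Section 8.2 speaks of patients accrued for each arm, which fits a non-randomised arm and keeps early failures. For the same reason the argument that the stage 1 ten are ambiguous is weak. But the accrual counts do not say how an unscanned patient is classified, so they anchor the denominator only in part.

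**Fewer patients are at risk of exclusion than first appears.** Section 6.2.3 asks for final-visit activities at discontinuation, Table 6 marks radiology at restaging or off study, and Section 6.2.2 images patients who stop for reasons other than progression every 12 weeks. Many early stoppers would be rescanned. The remainder are mainly deaths, withdrawals of consent and losses to follow-up before any scan. This stands.

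**The reversal depends on a second mismatch.** A reader might infer that two early deaths turn a failed arm into a success. But 6/29 fails only under the Section 8.3.2 interval rule. The cut-off implied by the stated alpha and power already counts 6/29 as a success, so removing two patients moves the interval rule back to the design's cut-off. This also stands, although the interval rule is the only final rule the plan writes down.

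**Conclusion.** The conflict is real and should be fixed before analysis. It is a should-fix point. The main gap is Arm C, where Section 8.3 as worded covers nobody and the 7.1.2 set could be used to raise the rate. The replacement footnote contradicts intention to treat wherever it is applied.

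The size is modest. The denominator decides the result only near the boundary, for example 6/29 (9.5%) against 6/27 (10.3%). With 5-15% never rescanned, the chance of success rises from 1.8% to 2.9-4.7% at a true 10% rate and from 74% to 77-81% at 30%. These figures assume that every dropped patient is a non-responder, that the stage 1 gate uses all accrued patients, and that the interval rule governs.

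The documents do not support the reading that this breaks the planned type I error. Over the assumed range the error stays within 0.0471, because the interval rule on all 29 patients is stricter than the design.

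**What to change.** 1. State in Sections 8.2, 8.3.1 and 8.3.2 that the stage 1 count, the final count and the ORR use all randomised patients in Arms A and B and all enrolled patients in Arm C.
2. Add that any patient without a post-baseline disease assessment counts as a non-responder.
3. In Section 7.1.2, label the evaluable set as supportive only.
4. Reconcile the replacement footnote in Section 5.1.1.1 with this denominator, so that replaced patients remain in the primary count.
5. Make the allocation statement in Section 8.0 agree with Section 3.6.

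The cost is wording only, with no change in sample size or procedures. The reported response rate may be slightly lower than on the evaluable set.
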